- The following protocol deviations may be considered major with the implication of data exclusion from the PP analysis population:
- A premature withdrawal, except for those who dropped out due to an insufficient treatment effect;
 - Missing primary variable value;
 - Violation of one or more inclusion/exclusion criteria (ineligibility);
 - Error in treatment assignment;
 - Use of excluded medication;
 - Use of Dilapan-S® or Foley catheter though contraindicated;
 - The subject does not deliver during the hospitalization in the study center.

These criteria will be updated and detailed in the SAP after the data review and before the clinical database has been frozen, without knowing the treatment assignment.

The PP population will be analysed according to their actual study treatment used (i.e. “as treated”). The PP population is the primary efficacy population.

Subject Disposition

All subjects screened and randomised will be accounted for. All post-randomisation discontinuations will be summarised by time of, and reason for, discontinuation. The number of subject screened and not randomised will be presented with the main reason for their non-inclusion.

The number of patients who were randomised will be reported. The patients with wrong assignment to treatment will be summarised by treatment and listed.

Patient Demographics and other Baseline Characteristics

Summary statistics of demographics, medical history, and other baseline characteristics will be presented by treatment group. The ARS population will be used.

Primary Efficacy Variable Analysis

Primary Efficacy Endpoint

The primary efficacy endpoint is the rate of overall vaginal delivery.

Statistical Hypothesis, Model and Method of Analysis

The primary hypothesis testing consists of simultaneous/combined tests for non-inferiority and superiority - a useful strategy proposed for a confirmatory phase III clinical trials [1] and accepted by EMA in 2000 (CPMP/EWP/482/99, PtC on switching between superiority and non-inferiority), provided that the non-inferiority margin has been defined in advance in the study protocol.

Statistical inference involves testing the hypotheses regarding the difference in proportions with a vaginal delivery between the Dilapan group and the foley group. For the non-inferiority test, this can be expressed as $H_{N0}: PD \leq PF - \delta$.

against the alternative $H_{NA}: PD > PF - \delta$.

Where PD and PF denote population proportions for Dilapan and foley group, respectively, and $\delta > 0$ is a non-inferiority margin. This type of test is called a test of non-inferiority.

If the purpose of the test is to prove the superiority of Dilapan to foley superiority, then

$H_{S0}: PD \leq PF$

will be tested against the alternative

$H_{SA}: PD > PF$

This setting generates the usual one-sided test of superiority.

These two tests can be performed simultaneously by employing the closed testing procedure (CTP) while controlling the overall type I error at the level α . In this special case, the resulting procedure is as follows:

1. First, the test of non-inferiority should be performed at the $\alpha=0.025$, one-sided. If H_{N0} is rejected, the test of superiority should be done at the $\alpha=0.025$, one-sided. Otherwise we can conclude that not even non-inferiority of Dilapan-S can be drawn.

2. In the test of superiority at the second step, if H_{S0} is rejected at the $\alpha=0.025$, one-sided, we should conclude that Dilapan-S is superior to the control. Otherwise non-inferiority can be concluded. It can be shown that this testing procedure is equivalent to a $(1-2\alpha)$ 2-sided confidence interval (CI) approach. The CI approach will be used in accordance with ICH E9 recommendations. The 95% 2-sided CI for Dilapan-S – Foley catheter difference will be calculated. A decision will be made as follows:

1. If the 95% CI is completely on the right side to the zero point, it will be concluded that Dilapan is superior over foley.

2. Otherwise, if the 95% CI is completely on the right side to the non-inferiority margin, it will be concluded that Dilapan-S is non-inferior to Foley catheter.

3. Otherwise no conclusion will be drawn.

For the non-inferiority test, the PP analysis population is often chosen as the primary population. To control type I error at the pre-specified level, the same population should be used for the superiority test within the frame of the closed testing procedure. As a result, PP set will be used for both tests as the primary analysis population. However, to demonstrate robustness to the alternative choice, the primary endpoint will also be performed using the ITT analysis population. The ITT analysis for the primary efficacy endpoint will be used to support the primary analysis using the PP population.

Secondary Variables Analysis

Rate of vaginal deliveries within 24 hours, rate of vaginal deliveries within 36 hours, rate of spontaneous vaginal deliveries, rate of operative vaginal deliveries and rate of caesarean sections will be analysed using similar statistical methods as described above for the primary endpoint, except for the definition of the non-inferiority margin and for the non-inferiority test. The 95% 2-sided CIs will be calculated for the treatment differences.

Time to reach active stage of labour defined as ≥ 6 cm (mins) will be analysed using survival analysis methods. Detailed methodology including set-up of censored values will be described in the final SAP. Change in Bishop score from baseline will be summarised by treatment group.

All rates above, time to reach active stage of labour and Bishop score are related to the secondary objectives and simultaneously, they are supportive measurements related to the primary objective. Patient satisfaction associated with the device used for cervical ripening (Patient Satisfaction Survey, question No. 12) will be evaluated as a secondary objective. Counts and proportions in all categories will be presented by treatment group. The location shift in response categories between the two treatment groups will be calculated and tested at the $\alpha = 0.05$ level of significance, two-sided.

Exploratory Variables Analysis

Exploratory variables will be summarised by treatment group.

Safety Variables Analysis

Safety variables will be summarised by treatment group.

Procedure for Accounting for Missing Data

Study subjects with missing primary variable will be evaluable neither for the ITT nor for the PPS population.

Missing primary variable data is expected to be very rare. If not, a different procedure may be refined in the SAP (e.g. a conservative imputation technique or sensitivity analyses) with the knowledge of the clinical data.

Procedure for Protocol Deviations

All protocol deviations will be listed by treatment group. Study subjects with a major protocol deviation will be excluded from the PPS analysis which makes demonstration of lack of sensitivity to protocol deviations possible (robustness).

Procedures for Deviations from the Original Statistical Plan

The SAP will contain more detailed description of the statistical analysis. If a need to change procedures of the analysis arises, an appropriate SAP update will be made. Major changes will require a protocol amendment.

Since the study is open-label, the risk of influencing the results has to be discussed in the report. A part of the final analysis will also be the originally planned analysis and its results will be provided in the report whenever technically possible. Every effort will be made to avoid such changes.

Particular attention will be paid to any differences between the planned analysis and the actual analysis as described in the protocol, protocol amendments or the updated statistical analysis plan based on a review of study data. Every effort will be made to avoid such deviations.

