Before the device placement, patients undergo continuous CTG monitoring for 20 minutes while fetal condition and uterine activity are monitored. The cervix is visualized with a sterile vaginal speculum and cleaned with iodine. As many as possible pieces of synthetic osmotic cervical dilator (Dilapan-S®, Medicem Technology, Kamenne Zehrovice, Czech Republic) are inserted into the cervical canal under direct visualization. Synthetic osmotic dilators are entered to the cervical canal with special attention to cross through the internal os. The number pieces inserted will vary, since different patients will have different pelvic or cervical exam/dilatation. Synthetic osmotic dilators will be inserted as per manufacturer's instructions for use /Appendix 2/. The patient will be instructed to report any excessive bleeding, pain or other concerns. Under no circumstances should patient try to remove Dilapan-S® herself.

The synthetic osmotic dilators will be left in place for at least 12 hours, and no longer than 24 hours. Patient will be allowed to ambulate, shower and perform regular activity as long as a reactive and reassuring NST is documented after placement of device. Reasons for examining or removing dilators earlier include: 1) Spontaneous onset of labor (defined as regular, firm, uterine contractions with an effaced cervix >80% and a cervical dilatation > 3 cm); 2) Category III fetal heart rate tracing; 3) Spontaneous rupture of membranes or need for amniotomy; 4) Spontaneous expulsion of dilators. If cervix remains unfavorable after extraction of the dilators (< 3cm and at most 60% effaced) to provide induction of labor, the second round of Dilapan-S® will be used in this case for maximum of 12 hrs. If cervix remains unfavorable after extraction of second round of cervical dilator, only pharmacological cervical ripening may be provided. Neither Dilapan-S® or Foley will be used in this case. The agent and its total dose will be recorded into the data sheet.

Group assigned to receive Foley catheter:

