The study will be explained as in the consent form and if agreed, subjects will elect either to or not to participate in the study after all risks and benefits are explained. Data to be collected will consist of age gravida/para, gestational age, BMI, time of date of intervention, time date of delivery, mode of delivery, bishop score at admission, bishop score after 12 hrs. of intervention, time and date of rupture of membranes, vaginal delivery within 24 hrs., hospital length of stay, other intrapartum and obstetrical interventions, complications in labor and delivery including but not limited to infections, hemorrhage, fetal decelerations and subject satisfaction. Data will be abstracted from subjects medical records as well as from direct interview with the subject. We will also collect basic neonatal data including birth weight, Apgar scores, rate of admission to neonatal intensive care unit, infections, and other neonatal complications. If elected to participate consents will be obtained and stored in subject chart. A copy of the consent will be given to the subject. Subjects will be consented in either English or Spanish by research personnel familiar with the language. Randomization will be done at time of consents. The study's time frame inclusive will be from 2016 till 2018. Data will be analyzed as per intent to treat.

Sample Size Calculation

The sample size will be calculated for the non-inferiority test.

The significance level of the test is targeted at 0.025, one-sided.

The rate of overall vaginal delivery is 71% and 76% for Foley catheter and Dilapan-S® , respectively. Higher rates are better.

The non-inferiority margin is $\delta=10\%$. It is defined as the largest treatment difference of no clinical importance.

The treatment allocation ratio will be 1:1.

The power of the non-inferiority test to be achieved is 90%.

Based on the above assumptions, the sample size would be 182 evaluable subjects in either treatment group, i.e. 364 evaluable subjects in total. Assuming that 13% of patients will not qualify for the primary analysis set (due to protocol deviation or considered as drop-out of loss to follow up), 420 patients are to be enrolled into this study.

5. Sub-Study Procedures: Not applicable.

6. Criteria for Inclusion of Subjects:

- Pregnant woman scheduled for induction of labor
- Age between 18 and 45 years
- Understanding and capable to sign informed consent
- Singleton pregnancy
- Gestational age ≥ 37 ^{0/7}weeks

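### The primary per-protocol set may exclude women who leave hospital undelivered, an exclusion that depends on the outcome and biases the comparison if such losses differ between arms

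*Combined protocol and SAP*

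**What the plan says.** All of this is in section 14 (Biostatistics) unless stated.

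- **Endpoint.** "The primary efficacy endpoint is the rate of overall vaginal delivery". No time limit is attached. Vaginal delivery within 24 and within 36 hours are separate secondary variables.
- **Primary set.** "The PP population is the primary efficacy population", and the text on the closed testing procedure uses it for both tests. ITT is supportive.
- **The bullet.** The PP list of deviations that can be treated as major ends with "The subject does not deliver during the hospitalization in the study center". It carries no exception. The later text on protocol deviations says that subjects with a major deviation are left out of PP.
- **A bullet pointing the other way.** The first item of the same list, premature withdrawal, exempts those who dropped out because the treatment effect was insufficient.
- **ITT.** Membership requires an available primary outcome. The same list of bullets is printed under the ITT heading, after a sentence about how that population will be used that is never completed.
- **Safeguards.** Classification is agreed in a documented meeting by people blinded to allocation. The criteria are to be updated after data review and before database freeze, without knowledge of assignment.
- **Treatment pathway (section 4).** Both arms allow a second round of the device, and then: "If cervix remains unfavorable after extraction of second round of cervical dilator, only pharmacological cervical ripening may be provided". Nothing states how a woman who still does not deliver is scored.

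**The concern.** A per-protocol set is meant to remove women whose treatment or eligibility departed from the plan. Not delivering in the study admission need not be such a departure. A woman can receive her allocated device, a second round and then pharmacological ripening, all as section 4 allows, and still leave undelivered. Her only deviation is then her result, and that result is closely tied to the endpoint.

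Excluding on a post-randomization result gives up the comparability that randomization provides. If undelivered departures are more common in one arm, that arm loses more women who had no vaginal delivery in the admission, and the difference in rates shifts. The set affected is the one that decides the trial. The plan also gives two answers for the same kind of woman: if she is recorded as withdrawn for insufficient effect she stays, and if she is recorded as undelivered she may go.

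**Working it through.** **1. The plan's own figure.** Inputs from the Sample Size Calculation in section 4: Foley 71%, Dilapan-S 76%, margin 10 points, one-sided alpha 0.025, power 90%, 1:1 allocation. With unpooled variance:

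n = (1.960 + 1.282)² × (0.71×0.29 + 0.76×0.24) / (0.05 + 0.10)² = 181.3, so 182 per arm, as stated. Inflating for 13% loss, 364/0.87 = 418.4, so 419 against the stated 420. The sample size is not at fault.

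**2. Effect of the exclusion on an arm's rate.** Let p be an arm's true rate when undelivered women count as no vaginal delivery, and u the share of the arm that leaves undelivered and is dropped. The PP rate becomes p/(1 − u), on 182(1 − u) women. The documents do not give u, so 0% to 5% per arm is an assumed range.

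**3. False non-inferiority at the margin.** Take Foley 71% and Dilapan-S 61%, a true difference of −10 points. With d the PP difference and SE its unpooled standard error, the probability of declaring non-inferiority is Φ((d + 0.10)/SE − 1.960).

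Example, 3% of Dilapan-S only: 0.61/0.97 = 0.629; d = 0.629 − 0.710 = −0.081; SE = 0.0495; Φ(0.381 − 1.960) = 5.7%.

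| Dropped, Foley / Dilapan-S (assumed) | PP difference (points) | False non-inferiority |
|---|---|---|
| 0% / 0% | −10.0 | 2.5% |
| 0% / 1% | −9.4 | 3.3% |
| 0% / 3% | −8.1 | 5.7% |
| 0% / 5% | −6.8 | 9.5% |
| 2% / 5% | −8.2 | 5.4% |
| 3% / 3% | −10.3 | 2.2% |
| 5% / 0% | −13.7 | 0.3% |

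**4. False superiority.** With both true rates at 71%, the probability is Φ(d/SE − 1.960). It is 6.7% at 0%/3% and 12.2% at 0%/5%, against 2.5% when the shares are equal.

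**5. In counts** (Wald 95% intervals, Dilapan-S minus Foley, 182 per arm before exclusion; the counts are chosen to lie close to the margin):

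- 126/182 v 129/182: −1.6 points (−11.1 to 7.8), not non-inferior.
- Three undelivered Dilapan-S women dropped, 126/179 v 129/182: −0.5 (−9.9 to 8.9), non-inferior.
- Three dropped from each arm, 126/179 v 129/179: −1.7 (−11.1 to 7.7), verdict unchanged.
- Three from Dilapan-S and one from Foley, 126/179 v 129/181: lower limit −10.3, verdict unchanged.

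**6. Dependence on scoring.** Steps 2 to 5 count every undelivered woman as a failure. Suppose instead that later deliveries count and a share v of the undelivered women later deliver vaginally. With p now including those deliveries, the rate after exclusion is (p − vu)/(1 − u). This exceeds p only when v < p. If v is larger than the arm's rate, exclusion lowers the rate.

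**The case against.** The strongest reply has four parts.

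- **Exclusion is permitted, not automatic, and is decided blind.** A reader might infer that every undelivered woman is removed. The wording does not say so. Blinding guards against choosing exclusions by arm, but it does not remove bias from a criterion that is itself an outcome. The discretion also leaves the rule unsettled until after data review.
- **The endpoint has no time limit.** A reader might infer that the exclusion can only raise an arm's rate. That holds only if delivery outside the study admission is counted as failure, which the plan does not say. In the example, if two of the three undelivered Dilapan-S women later delivered vaginally, the full comparison would be 128/182 v 129/182: −0.5 points (−9.9 to 8.8). That is already non-inferior with nobody excluded. This part stands, and it is why the scoring has to be fixed in advance.
- **The distortion needs unequal losses.** Nothing in the documents suggests that Dilapan-S would have more undelivered departures than Foley. With equal losses the effect is small and slightly conservative at the margin. This stands too.
- **The group may be small or mixed.** Section 13 equates failed induction with cesarean delivery, and a cesarean in the same admission stays in PP as a failure. No section describes discharge after a failed induction, and the bullet may also catch women who leave for other reasons or deliver elsewhere. This limits the likely size but does not justify the bullet.

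ITT is not a sure remedy. It is only supportive, it needs the outcome to be available, and the repeated list under its heading leaves its membership unclear. A reader might conclude that ITT excludes these women as well. The unfinished sentence does not establish that.

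**Conclusion.** The concern holds as a defect in the definition of the primary set. The plan permits exclusion on a post-randomization result tied to the endpoint, contradicts its own exemption for insufficient effect, and never says how an undelivered woman is scored.

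The bias can go either way. Over the assumed range of 0% to 5%, the false non-inferiority rate runs from 0.3% (5% of Foley only) to 9.5% (5% of Dilapan-S only), around the nominal 2.5%. These figures assume 182 per arm before exclusion, true rates at the margin, and undelivered women counted as failures and all dropped. The true frequency is unknown and may be low, so the actual effect may be small. The documents do not support saying that the trial is tilted toward Dilapan-S, or that treatment failures are routinely removed. The point deserves correction because a handful of women, lost unequally, could change a close verdict, and the correction is cheap.

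**What to change.** 1. Delete the non-delivery bullet from the PP list in section 14, and from the repeated list under the ITT heading. Complete the unfinished ITT sentence at the same time.
2. State that a woman who received a study device and leaves the study hospitalization undelivered stays in PP and ITT, and counts as no vaginal delivery in the primary analysis. This also brings the list into line with its exemption for insufficient effect.
3. Add a sensitivity analysis that scores her by her later mode of delivery where the chart gives it.
4. Settle this before data review, because the endpoint has no stated time limit and either scoring could otherwise be chosen once outcomes are visible. Report the number of such women by arm.

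**Cost.** A few lines of text and one extra analysis. The design calculation stays at 182 per arm on the stated rates. Both arms' observed rates may fall slightly below the 71% and 76% used for planning, which are stated for overall delivery. Because the list is protocol text and section 14 requires an amendment for major changes, a short protocol amendment may be needed.

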3. Concise Summary of Project: Primary outcome will be to compare the efficacy of achieving a vaginal delivery using the synthetic osmotic cervical dilator Dilapan-S® versus Foley catheter for cervical ripening prior to induction of labor. Secondary outcomes will be to evaluate the efficacy of Dilapan-S® versus Foley catheter on other clinical outcomes such as vaginal delivery rate within 24 and 36 hours post insertion, time to reach active stage of labor defined as ≥ 6 cm, change in Bishop score, rate of spontaneous and operative vaginal delivery, rate of caesarean sections and patient satisfaction. Randomization will be performed using a computer generated random list of numbers assigning subjects to the 2 groups of the study. This list of random number assignments will be kept secure in an opaque envelope until the end of the study.

4. Study Procedures:

After institutional review approval, pregnant women that are scheduled for induction of labor will be approached by principal investigator or any of the co-investigators for participation in the study in a private subject room in labor and delivery unit. Prospective subjects presenting for induction of labor in labor and delivery, and willing to participate in the study will be evaluated for their eligibility including, including their bishop score. The latter will be obtained from the subject chart after the initial pelvic exam which is standard of care for these subjects in our unit. After obtaining informed consent, subjects will be randomized.

Group assigned to receive synthetic osmotic cervical dilator:

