- Live fetus in cephalic presentation
- Intact membranes
- Pelvic exam (sterile vaginal exam) of less than or equal to 3cm and at most 60% effaced.

7. Criteria for Exclusion of Subjects:

- Iodine allergy
- Active labor or oxytocin has been administered
- Chorioamnionitis
- Prior uterine or cervical surgery
- Non reassuring fetal status requiring immediate delivery
- Non-cephalic fetal presentation
- Active vaginal bleeding from cervical os
- Placenta previa
- EFW > 5000 gm (non diabetic) or > 4500gm (diabetic)
- ⚡ Other contraindication to vaginal delivery

8. Sources of Research Material: Medical chart/records.

9. Recruitment Methods and Consenting Process: After institutional review approval, pregnant women scheduled for induction of labor will be approached by perinatal research division staff (PRDS) for participation in the study. Prospective subjects presenting for induction of labor in labor and delivery unit, and willing to participate in the study will be evaluated for their eligibility including their pelvic

exam. The latter will be obtained from the subject chart after the initial pelvic exam which is standard of care for these subjects in our unit. The study will be explained as in the consent form and if agreed, subjects will elect either to or not to participate in the study after all risks and benefits are explained. If willing to participate, written consent will be obtained and a copy placed in patient chart. A copy of the consent will be given to the subject. Subjects will be consented in either English or Spanish by research personnel familiar with the language. Randomization will be done after obtaining consent. Participants are randomly allocated to cervical ripening with either a synthetic Dilapan-S® or Foley catheter. The randomization sequence is created using a computer generated randomization scheme with 1:1 allocation for each arm of the study. The random allocation sequence is concealed from those responsible for recruiting participants into the study by keeping it in a file cabinet with access restricted to research staff. PRDS will disclose the nature of the assignment only after patient's consent.

10. Potential Risks:

- a. Accidental release of confidential subject information
- b. Vaginal bleeding during/after study device's insertion
- c. Subjective pain felt during insertion
- d. Vaso-vagal reaction from manipulation of the cervix
- e. Contamination of the device during insertion

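### Improvement, not an error: the primary and secondary rate comparisons use no baseline covariate, although a pre-specified standardised risk difference could narrow the interval modestly at little cost

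*Combined protocol and SAP*

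**What the plan says.** Under Statistical Hypothesis, Model and Method of Analysis (section 14), the primary endpoint is handled as follows: "Statistical inference involves testing the hypotheses regarding the difference in proportions with a vaginal delivery between the Dilapan group and the foley group". A 95% two-sided interval for Dilapan-S minus Foley is read against zero and against the 10-point margin. Secondary Variables Analysis carries similar methods over to five further rates: vaginal delivery within 24 hours and within 36 hours, spontaneous vaginal delivery, operative vaginal delivery, and caesarean section. No covariate, stratification factor or model is named for any of them. Section 9 describes a 1:1 computer-generated list, also without a stratification factor.

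The covariates are nevertheless collected. Section 4 states "Data to be collected will consist of age gravida/para, gestational age, BMI" and, further on in the same list, "bishop score at admission, bishop score after 12 hrs. of intervention". Their stated or implied uses are:

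- eligibility, where women are "evaluated for their eligibility including, including their bishop score";
- description, where "Summary statistics of demographics, medical history, and other baseline characteristics will be presented by treatment group";
- a summary of change in Bishop score.

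Section 14 defers fuller detail to a later SAP, but nothing in the text promises adjustment.

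**The concern.** The trial turns on whether an interval with a half-width of about 9 points clears a 10-point margin. If parity, Bishop score and BMI predict vaginal delivery, a crude comparison leaves that variation in the error term. A standardised risk difference could remove part of it with no additional women and no new data items. It is on the same scale as the margin, so the decision rule would not change. A conditional odds ratio would not have that property.

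**Working it through.** **Inputs from the Sample Size Calculation.** One-sided alpha is 0.025, power is 90%, the margin is 10 points and allocation is 1:1. On rates: "The rate of overall vaginal delivery is 71% and 76% for Foley catheter" and Dilapan-S respectively. On size: "the sample size would be 182 evaluable subjects in either treatment group".

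**1. Reproduce the plan's figure.** With unpooled variance,
n = (1.95996 + 1.28155)² × (0.71×0.29 + 0.76×0.24) / (0.05 + 0.10)² = 10.507 × 0.3883 / 0.0225 = 181.3, so 182 per arm and 364 in total. Then 364/0.87 = 418.4, which is consistent with the 420 to be enrolled.

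**2. Crude precision at 182 per arm.** SE = √(0.3883/182) = 0.0462. Half-width = 1.96 × 0.0462 = 0.0905. Power = Φ(0.15/0.0462 − 1.96) = 90.1%. If both true rates are 71%, power = Φ(0.10/√(2×0.71×0.29/182) − 1.96) = 55.7%.

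**3. What adjustment does, approximately.** If the covariates explain a share R² of the within-arm outcome variance, and the variance carries an n/(n−5) correction for five model parameters, the half-width is multiplied by about √((1−R²) × 364/359). Break-even is R² = 1 − 359/364 = 1.4%.

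- R² = 0: √1.0139 = 1.007, or 0.7% wider.
- R² = 1.1% (weak): √(0.989×1.0139) = 1.001, essentially no change.
- R² = 7.6% (moderate): √(0.924×1.0139) = 0.968, or 3.2% narrower.
- R² = 14.9% (strong): √(0.851×1.0139) = 0.929, or 7.1% narrower.

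**4. Simulation.** There were 20,000 trials per scenario, with 182 women per randomised arm. Half the women are nulliparous, Bishop score and BMI are standard normal, and intercepts are set to give the stated rates. The crude analysis uses a Wald interval. The adjusted analysis uses a logistic model standardised to a risk difference, with a sandwich SE and the n/(n−5) correction. All odds ratios are **assumptions**, because the documents give none.

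| Odds ratios: parity / Bishop per SD / BMI per SD | Half-width in points at 71% vs 76%, crude → adjusted | Change in width | Power, 71% vs 76% | Power, 71% vs 71% |
|---|---|---|---|---|
| 1 / 1 / 1 (none) | 9.03 → 9.09 | 0.7% wider | 90.0 → 89.6% | 55.5 → 55.0% |
| 1.5 / 1.1 / 1.1 (weak) | 9.03 → 9.04 | none | 90.0 → 90.1% | 56.1 → 56.0% |
| 2 / 1.2 / 1.2 | 9.02 → 8.93 | 1% narrower | 90.1 → 90.6% | 55.9 → 57.2% |
| 3 / 1.3 / 1.3 (moderate) | 9.02 → 8.73 | 3% narrower | 90.0 → 91.8% | 55.2 → 58.6% |
| 4 / 1.4 / 1.4 | 9.02 → 8.55 | 5% narrower | 90.0 → 93.2% | 55.3 → 60.3% |
| 5 / 1.5 / 1.5 (strong) | 9.02 → 8.38 | 7% narrower | 90.1 → 94.0% | 55.6 → 62.6% |

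Mean crude and adjusted estimates agree (0.050), and coverage is 94.7% to 95.2%. Type I error at the margin (71% vs 61%) is 2.4% to 2.7% crude and 2.3% to 2.6% adjusted. For superiority at 71% vs 71% it is 2.5% to 2.6% crude and 2.4% to 2.6% adjusted.

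**5. Size in women.** Moderate: 182 × ((0.0902/0.0873)² − 1) = 12 more evaluable women per arm. Strong: 182 × ((0.0902/0.0838)² − 1) = 29.

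**6. Sensitivity.** Entry is limited to "Pelvic exam (sterile vaginal exam) of less than or equal to 3cm and at most 60% effaced", which may blunt the Bishop score. With no Bishop effect at all, the gain is 2.6% (moderate) and 6.0% (strong). With 10% of Bishop and BMI values missing and set to the pooled mean, it is 3.1% and 6.8%. With 30% nulliparous it is 3.2% and 7.5%; with 70%, 2.4% and 5.4%.

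**7. Secondary rates.** At assumed rates of 50%, 30% and 10%, the interval narrows by 4.3%, 3.5% and 1.2% (moderate) or 9.1%, 7.7% and 3.2% (strong). It is 0.7% wider when nothing is prognostic, and within 0.4% of no change when the covariates are weak.

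**The case against.** The strongest reply is that nothing is broken. An unadjusted risk difference that matches its own sample-size basis is a legitimate choice, and the design names no stratification factor that would oblige adjustment. This stands, and it is why the point is an improvement only.

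Second, the benefit cannot be established from the documents. The assumed range includes a small loss and no change, and the larger gains need assumed parity odds ratios of 3 to 5. This also stands, so the gain must be stated as conditional.

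Third, a later SAP might already include adjustment. It might, but the present text names none and promises none, so the deferral does not settle the matter.

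Fourth, the simulation describes randomised arms and a correctly specified model. The plan's primary set is per-protocol, grouped by treatment actually used. There, crude and adjusted estimates need not agree, and the coverage and type I error results do not carry over automatically. This stands in full. The evidence applies most directly to an ITT-like comparison.

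A reader might also infer that adjustment rescues the trial if Dilapan-S has no real advantage. It does not. The power of about 56% at equal rates comes from the assumed 5-point advantage in the sample size calculation. Adjustment lifts it only to 58.6% (moderate) or 62.6% (strong).

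**Conclusion.** The point holds as an improvement. The plan collects three plausible baseline covariates and uses none of them in the rate comparisons. Depending on assumed prognostic strength, adjustment changes the primary interval from 0.7% wider to about 7% narrower, with about 3% narrower in the moderate case. At the design rates, non-inferiority power moves from about 90% to between 89.6% and 94.0%. The conclusion rests on the assumed odds ratios, half the women being nulliparous, 182 evaluable women per arm and arms as randomised.

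The documents do not support the stronger reading that the crude analysis is invalid or the sample size wrong: the stated 182 per arm reproduces exactly. Nor would adjustment repair selection into the per-protocol, as-treated set.

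**What to change.** Pre-specify, by protocol amendment or in the SAP, a logistic model with arm, parity (0 vs 1 or more), admission Bishop score and BMI. Standardise it to a marginal risk difference with a robust 95% interval, and keep the cut-offs at -10 points and zero. In addition:

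- Apply it to both the PP and ITT sets, and state that its validity argument is cleanest for ITT.
- Fill missing Bishop score and BMI with the mean, and missing parity with the commonest category, pooled over arms. Imputation of parity was not simulated.
- Revert to the crude difference if the model does not converge, and always report the crude difference as a sensitivity analysis.
- Use the same model for the five secondary rates. A minimum-events rule (for example 30) for reverting to the crude difference is optional. The simulations do not show a need for one: at an 8% rate (0.08 × 364, about 29 events), the adjusted interval was still 0.9% (moderate) or 2.6% (strong) narrower, and adjusted coverage across the secondary-rate runs was 94.6% to 95.3%.

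Timing matters. The model should be final before the blinded data review and database freeze, and before anyone sees outcome data by arm. Tying it only to unmasking is not enough, because section 14 places unmasking after the analysis and describes the study as open-label.

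The cost is SAP wording and probably an amendment, since section 14 requires one for major changes and replacing the primary estimator plausibly is one. No new data items or extra women are needed. The statistical downside is a loss of precision under 1% if the covariates are not prognostic.
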